2.3.2 Secondary Endpoints

2.3.2.1 Secondary Endpoint #1: the composite responder rate at 6 months, between groups.

A subject is considered a composite responder if the following criteria are met:

- Improvement in function, defined as a 13%-point decrease on ODI or score $\leq 20\%$,
- OR
- Improvement in pain, defined as a $\geq 50\%$ decrease on Numerical Rating Scale (NRS)

The hypothesis test:

$$H_0: P_{\text{Composite_SCS}} = P_{\text{Composite_CMM}}$$

$$H_a: P_{\text{Composite_SCS}} \neq P_{\text{Composite_CMM}}$$

$P_{\text{Composite_SCS}}$ and $P_{\text{Composite_CMM}}$ denote the composite responder rate for SCS and CMM groups, respectively.

2.3.2.2 Secondary Endpoint #2: the relative NRS change from baseline to 6 months between groups

The relative NRS change is defined as:

$$\Delta NRS = \frac{(NRS_{\text{Baseline}} - NRS_{6 \text{ months}})}{NRS_{\text{Baseline}}} \times 100\%$$

The hypothesis test:

$$H_0: \Delta NRS_{\text{SCS}} = \Delta NRS_{\text{CMM}}$$

$$H_a: \Delta NRS_{\text{SCS}} \neq \Delta NRS_{\text{CMM}}$$

ΔNRS_{SCS} and ΔNRS_{CMM} denote the relative NRS change for SCS and CMM groups, respectively.

2.3.2.3 Secondary Endpoint #3: the ODI change from baseline to 6 months

The ODI score is calculated as:

$$ODI = \frac{\text{Total ODI score}}{(5 \times (\text{number of non missing questions}))} \times 100\%$$

Change of ODI is calculate as: $\Delta ODI = ODI_{\text{Baseline}} - ODI_{6 \text{ months}}$

The hypothesis test:

$$H_0: \Delta ODI_{\text{SCS}} = \Delta ODI_{\text{CMM}}$$

$$H_a: \Delta ODI_{\text{SCS}} \neq \Delta ODI_{\text{CMM}}$$

ΔODI_{SCS} and ΔODI_{CMM} denote the change from baseline to 6 months for SCS and CMM groups, respectively.

Statistical Analysis Plan

2.3.2.4 Secondary Endpoint #4: PCS responder rate

PCS responder is defined as: subjects that are either clinically catastrophizing on PCS at baseline (PCS score ≥ 30) and report a score of < 30 at 6 months follow up or report a 40% decrease in score at 6 months follow-up compared to baseline regardless their baseline scores.

The hypothesis test:

$$H_0: P_{PCS_SCS} = P_{PCS_CMM}$$

$$H_a: P_{PCS_SCS} \neq P_{PCS_CMM}$$

P_{PCS_SCS} and P_{PCS_CMM} denote the PCS responder rate for SCS and CMM groups, respectively.

2.3.2.5 Secondary Endpoint #5: PGIC responder rate

PGIC responder is defined as: PGIC is 'Better' or 'Great Deal Better' at 6 months.

The hypothesis test:

$$H_0: P_{PGIC_SCS} = P_{PGIC_CMM}$$

$$H_a: P_{PGIC_SCS} \neq P_{PGIC_CMM}$$

P_{PGIC_SCS} and P_{PGIC_CMM} denote the PGIC responder rate for SCS and CMM groups, respectively.

2.3.2.6 Secondary Endpoint #6: the relative change of PI from baseline to 6 months between groups

The relative PI change is defined as:

$$\Delta PI = \frac{(PI_{Baseline} - PI_{6\ months})}{PI_{Baseline}} \times 100\%$$

The hypothesis test:

$$H_0: \Delta PI_{SCS} = \Delta PI_{CMM}$$

$$H_a: \Delta PI_{SCS} \neq \Delta PI_{CMM}$$

ΔPI_{SCS} and ΔPI_{CMM} denote the relative PI change for SCS and CMM groups, respectively.

2.3.2.7 Secondary Endpoint #7: the relative change of PF from baseline to 6 months between groups

The relative PF change is defined as:

$$\Delta PF = \frac{(PF_{6\ months} - PF_{Baseline})}{PF_{Baseline}} \times 100\%$$

The hypothesis test:

$$H_0: \Delta PF_{SCS} = \Delta PF_{CMM}$$

$$H_a: \Delta PF_{SCS} \neq \Delta PF_{CMM}$$

ΔPF_{SCS} and ΔPF_{CMM} denote the relative PF change for SCS and CMM groups, respectively.

Statistical Analysis Plan

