6.6.2.5 Oswestry Disability Index (ODI)

The ODI is an index derived from the Oswestry Low Back Pain Questionnaire used by clinicians and researchers to quantify disability for low back pain (26). The self-completed questionnaire contains ten topics concerning intensity of pain, lifting, ability to care for oneself, ability to walk, ability to sit, sexual function, ability to stand, social life, sleep quality, and ability to travel. Each topic category is followed by 6 statements describing different potential scenarios in the subject's life relating to the topic. The subject checks the statement which most closely resembles their situation. Each question is scored on a scale of 0-5 with the first statement being zero and indicating the least amount of disability and the last statement is scored 5 indicating most severe disability. The scores for all questions answered are summed, divided by the total possible score based on the number of questions answered and converted to a percentage. Zero is equated with no disability and 100 is the maximum disability possible. Five different levels of disability are defined within that range; minimal (0%-20%), moderate (21%-40%), severe (41%-60%),

Clinical Investigation Plan

crippling (61%-80%), and bed bound or exaggerated symptoms (81-100%). A decrease of 13% or more on the 0%-100% scale demonstrates a meaningful, clinical improvement in disability (27).

6.6.2.6 Patient-Reported Outcome Measure Information System (PROMIS) 29

The PROMIS-29 is a 29-item profile instrument developed in partnership with the National Institutes of Health (NIH) to estimate overall quality of life by assessing 7 health domains known to impact activities of daily living: depression, anxiety, physical function, pain interference, fatigue, sleep disturbance, and social function. The final item is an 11-point pain intensity numerical rating scale (NRS). Subjects should read each item and check the one box that most closely represents their response. Each item is scored on a scale from 1-5 with total scores for each domain ranging from 4-20. Greater scores represent more of whatever concept is being measured (e.g., depression or physical function). Scoring tables have been provided in the measure manual. Raw domain scores are converted to t-scores with a mean of 50 and a standard deviation of 10.

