1.4.2 Secondary Endpoints

- Secondary Endpoint #1: the composite responder rate, based on NRS or ODI improvements, at 6 months between groups. A subject is considered a composite responder if the following criteria are met:
 - Improvement in function, defined as a 13%-point decrease on ODI or score $\leq 20\%$,
 - Improvement in pain, defined as a $\geq 50\%$ decrease on Numerical Rating Scale (NRS)
- Secondary Endpoint #2: the relative change on NRS from baseline to 6 months between groups
- Secondary Endpoint #3: the ODI change from baseline to 6 months between groups
- Secondary Endpoint #4: the PCS responder rate at 6 months between groups
- Secondary Endpoint #5: the Patient Global Impression of Change (PGIC) at 6 months between groups
- Secondary Endpoint #6: the relative change from baseline to 6 months for Pain Interference (PI) from PROMIS-29 between groups
- Secondary Endpoint #7: the relative change from baseline to 6 months for Physical Function (PF) from PROMIS-29 between groups

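### Secondary endpoints #6 and #7 take percent change of PROMIS-29 scores that have no true zero and do not name the metric; T-score points would be interpretable

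*SAP*

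**What the plan says.** SAP 1.4.2 lists, as the last two of seven secondary endpoints, "the relative change from baseline to 6 months for Pain Interference (PI) from PROMIS-29 between groups" and "the relative change from baseline to 6 months for Physical Function (PF) from PROMIS-29 between groups". SAP 2.3.2.6, headed "the relative change of PI from baseline to 6 months between groups", and SAP 2.3.2.7, its PF counterpart, give the formulas. PI change is (baseline − 6 months) / baseline × 100%. PF change is (6 months − baseline) / baseline × 100%. Both are therefore signed so that positive means improvement. Neither section says whether raw or T-scores go into the formula.

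Protocol 6.6.2.6 describes both metrics. For raw scores: "Each item is scored on a scale from 1-5 with total scores for each domain ranging from 4-20". It then adds: "Raw domain scores are converted to t-scores with a mean of 50 and a standard deviation of 10". Higher means more of the concept, so high PI is bad and high PF is good. SAP 3.5.1 sets its descriptive PROMIS responder limits in T-scores (60 or below, 40 or above) and adds an MCID component taken from the literature.

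Two neighbouring endpoints are useful comparisons. Endpoint #2 is percent change on the NRS, where Protocol 6.6.2.3 defines 0 as no pain. Endpoint #3 is absolute change on the ODI (SAP 2.3.2.3).

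SAP 2.2.1 specifies a two-sample t-test or Wilcoxon test for continuous data. SAP 2.11 tests the secondary endpoints in fixed order at two-sided 5%, with #6 and #7 last. Table 1 in SAP 2.4 gives detectable differences of 7.2 (SD 15) for #6 and 12.0 (SD 25) for #7.

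**The concern.** A percentage of baseline means something when zero is absence of the thing measured, as on the NRS. A T-score of zero is not absence of pain interference or of physical function; it lies five SDs below the reference mean. Dividing by the baseline T-score therefore divides by a number fixed by a scaling convention. The raw score has a minimum of 4, so it does not escape the problem.

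Three things follow.

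- The same change in T-score points receives a different percentage at each baseline.
- The denominator is large for a severely affected subject on PI and small for one on PF, so adjacent endpoints from one instrument weight severity in opposite directions.
- A percent result cannot be turned into T-score points without knowing the baselines, so it cannot be read directly against a T-score MCID.

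Because the metric is unnamed, two analysts could also follow the same formula and report different estimates for a tested endpoint.

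**Working it through.** **Inputs.** From the documents: the formulas (SAP 2.3.2.6 and 2.3.2.7); T-score mean 50, SD 10 and raw range 4–20 (Protocol 6.6.2.6); 80 SCS and 60 CMM, 80% power, and the Table 1 values (SAP 2.4); two-sided 5% (SAP 2.11). Assumed, because the documents give no PROMIS baselines or SDs in T-score points: PI baselines of 55–75, PF baselines of 25–45, and the simulation settings below.

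**Step 1: reproduce Table 1.** Detectable difference = (1.960 + 0.842) × SD × √(1/80 + 1/60) = 2.802 × 0.1708 × SD = 0.478 × SD.

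- #6: 0.478 × 15 = 7.18 (7.23 by noncentral t), stated as 7.2.
- #7: 0.478 × 25 = 11.96 (12.05 by noncentral t), stated as 12.0.

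Both rows reproduce, and both are 0.48 SD (7.2/15 = 12.0/25 = 0.48).

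**Step 2: the same 5-point gain at different assumed baselines.**

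| Domain | Worse baseline | Better baseline |
|---|---|---|
| PI | 5/70 = 7.1% | 5/55 = 9.1% |
| PF | 5/30 = 16.7% | 5/45 = 11.1% |

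The subject who starts worse gets the smaller percentage on PI and the larger one on PF.

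**Step 3: raw scores behave the same way.** A fall from 16 to 12 is 4/16 = 25.0% on the 4–20 scale. Scored 0–16 it is 4/12 = 33.3%.

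**Step 4: Table 1 in T-score points.** At assumed PI baselines of 60–70, 7.2% is 4.3–5.0 points. At assumed PF baselines of 30–40, 12.0% is 3.6–4.8 points. The rows look far apart, but in T-score points they are similar; at these baselines the gap comes largely from the denominators.

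**Step 5: the ordering of arms can change.** In a constructed PI example, arm A goes 60→58 and 75→66.5, and arm B goes 60→52 and 75→73.

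- Mean point change: A (2 + 8.5)/2 = 5.25; B (8 + 2)/2 = 5.00.
- Mean percent change: A (3.3 + 11.3)/2 = 7.3%; B (13.3 + 2.7)/2 = 8.0%.

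This shows only that the two definitions are different estimands. It says nothing about how often they would disagree.

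**Step 6: effect on the test** (simulation, 4,000 trials per setting, 80/60, assumed mean baselines PI 65 and PF 36).

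*(a) Change independent of baseline, baseline SD 5; effect 4.7 points with change SD 9.75 (PI), 4.3 with change SD 9 (PF).* Power for percent against absolute change was 79.4% v 79.7% (PI) and 78.3% v 79.2% (PF). With no effect, percent change rejected in 4.3% (PI) and 5.3% (PF) of trials. Under these effects, the two definitions gave different significance calls in 1.8% (PI) and 3.3% (PF) of trials.

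*(b) Effect 4 points, 6-month SD 8, baseline SD 5–7, baseline-to-6-month correlation 0.3–0.5.* Approximate power at the two extremes:

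| Setting | Domain | Percent | Absolute | ANCOVA |
|---|---|---|---|---|
| SD 5, correlation 0.5 | PI | 92% | 92% | 92% |
| SD 5, correlation 0.5 | PF | 90% | 92% | 92% |
| SD 7, correlation 0.3 | PI | 74% | 74% | 86% |
| SD 7, correlation 0.3 | PF | 67% | 74% | 86% |

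Against absolute change, percent change lost about 1.5 to 7 points for PF and essentially nothing for PI.

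**The case against.** The strongest reply is that the scale is fixed and the formulas are pre-specified. Nobody proposes to re-centre or reverse the T-score, the tests are two-sided, and randomisation protects the null. Most of that stands. A reader might infer that the p-values or the type I error cannot be trusted; the documents do not support this, and simulated rejection under the null stayed near 5%. The one choice left open is raw or T-score, which the formula sections do not settle.

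A reader might also infer a sign error from the opposite directions of the two scales. There is none: the SAP reverses the subtraction for PF. Only the weighting by baseline severity differs.

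A third tempting reading is that dividing by baseline adds noise to both endpoints. Against absolute change, the assumed settings show a loss for PF and essentially none for PI.

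It is also fair to say that interpretable results will exist elsewhere. Protocol 4.3 and SAP 3.5.1 plan PROMIS-29 change from baseline at each visit and a responder analysis that uses MCIDs. Those are descriptive, however, whereas #6 and #7 carry the hypothesis tests.

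Finally, the stakes are limited. No later test depends on #7, study success rests on the primary endpoint alone (SAP 2.7), and the sample size re-estimation covers only the primary endpoint and #1 to #3 (SAP 2.4 and 2.5).

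**Conclusion.** The point holds as a matter of interpretability and specification, and it should be fixed. The metric for #6 and #7 is not named. On either candidate metric, the percent effect depends on an arbitrary origin and weights severity oppositely in the two domains. In the assumed baseline ranges, the same 5 points vary from 7.1% to 9.1% for PI and from 11.1% to 16.7% for PF. The validity of the tests, study success and the sample size are not affected.

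This rests on T-scores being intended, which is inferred from Protocol 6.6.2.6 and SAP 3.5.1. The origin problem survives if raw scores were meant. The sizes rest on assumed baselines; eligibility at NRS 6 or more and ODI 30% or more might narrow the real spread, and the documents cannot settle that. The PF power loss, about 1 to 7 points across the settings tried, depends on the assumed baseline spread and correlation.

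**What to change.** 1. State in SAP 2.3.2.6 and 2.3.2.7 that PI and PF are T-scores.
2. Define each endpoint as the between-arm difference at 6 months in T-score points. ANCOVA adjusting for the baseline T-score is preferable; PROMIS-29 is already collected at baseline (Protocol 6.2.2), and ANCOVA had at least as much power as percent change in the settings tried. The minimum is absolute change, as for ODI in #3, which cures the defect without leaving the tests in SAP 2.2.1.
3. Restate rows #6 and #7 of Table 1 in T-score points with a stated SD. For absolute change the detectable difference stays at 0.478 SD: 3.3, 3.8, 4.3 or 4.8 points for an assumed SD of change of 7, 8, 9 or 10. If ANCOVA is chosen, use the residual SD given baseline instead.

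The cost is SAP wording plus one SD assumption per domain, which the documents do not supply. No new data are needed, and sample size, the interim re-estimation and the order of testing are unchanged. The amendment should be made before the primary analysis; SAP 1.6 keeps sponsor statisticians from outcome data by arm until then.

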2.4 Sample Size/Power Calculations

The study was designed to enroll approximately 200 subjects in Phase I and up to 70 subjects in Phase II. The following assumptions are used in the power calculation for the primary endpoint:

- Assumed response rate of 45% for the SCS group and 20% for the CMM group
- 3:2 (SCS:CMM) randomization ratio
- 25% attrition rate to primary endpoint (6 months) follow-up in both groups
- Two-sided alpha of 0.05
- Z-test with unequal variance

Based on the assumptions above, there is at least 90% power to evaluate the primary endpoint with the Phase I cohort.

The minimum detectable differences for secondary endpoints using phase I PTE cohort (assume approximately 80 SCS and 60 CMM) with 80% power are shown in Table 1 below.

Table 1: Minimum Detectable Differences (MID) for Secondary Endpoints

Secondary Endpoints	MID (standard deviation for each group)
#1: Composite Responder	23%
#2: Relative NRS Change in %	16.9(35)
#3: ODI Change	7.2 (15)
#4: PCS Responder	21%
#5: PGIC (%)	23%
#6: Relative Pain Interference Change in %	7.2 (15)
#7: Relative Physical Function Change in %	12.0 (25)

The sample size re-estimation will be based on the interim analysis (IA) population (Adaptive Design Plan CL1014964). The unblinded independent statistician will perform the sample size re-estimation for 4 endpoints (1 primary and secondary endpoints #1, #2, and #3) and generate a recommendation if more subjects are needed to meet the statistical significance of each endpoint.

The power calculation was performed using PASS 15 (NCSS LLC).⁵

2.5 Interim Analysis

Interim analysis for sample size re-estimation will be considered to determine the sample size and the timing of primary analysis. There is one planned interim analysis which will be conducted when 70% of the Phase I randomized subjects reach/or complete the 6-month visit. If the sample size is increased, the CHW weighted statistic⁶ will be used in the final analysis of the primary and secondary endpoints 1, 2, and 3. Details are be shown in Adaptive Design Plan CL1014964. .

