1.3 Clinical Investigation Design

This is a prospective, multi-center, randomized, controlled clinical trial with an optional crossover component. It is designed to evaluate the efficacy of BurstDR™ Spinal cord stimulation (SCS) in the treatment of chronic axial low back pain with a neuropathic component, compared with comprehensive medical management (CMM).

Subjects will be followed in-clinic for required study visits at 1,3, 6, 9, 12, 18 and 24 months and via phone call or optional clinic visit at 15- and 21-months. Due to the individualized nature of study therapies, patient reported outcomes will be continually assessed and additional patient outreach conducted in order to determine if therapy adjustment(s) are warranted to optimize pain control. The primary endpoint will be assessed at the 6-month follow-up visit. Upon completion of the 6-month follow-up visit, subjects who are dissatisfied with therapy and receiving inadequate improvement with their treatment assignment will be allowed to cross-over to the other treatment arm, if desired per Cross Over Instructions (CL1014686).

Up to 270 subjects will be randomized in the study which is split into two phases. Phase I will include the first minimal 200 randomized subjects. Phase II is the continued access phase and will include up to 70 randomized subjects.

Subject enrollment is expected to be completed within 18 months; subjects will be followed for 2 years. The total duration of the study is expected to be approximately 4 years, including enrollment, data collection from all subjects, and study close out.

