2.2 Statistical Methods

2.2.1 Analysis of Continuous Data

For continuous variables (e.g., age, etc.), results will be summarized as number of observations, means, and standard deviations, and where applicable, with quartiles, minimums, maximums, and 95% confidence intervals for the means. Difference between two groups, when specified, will be summarized with difference of the two means, and the 95% confidence interval of the differences. The p-values will be calculated based on either two-sample t-test or Wilcoxon rank sum test as appropriate.

Cumulative distribution function (CDF) may be used in displaying a continuous plot of the percent change from baseline on the horizontal axis and the cumulative percent of patients experiencing up to that change on the vertical axis. Kolmogorov-Smirnov test may be used to test whether two empirical distributions are different using proc npar1way in SAS®¹.

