2.2.2 Analysis of Categorical Data

For categorial variables (e.g. gender, etc.), results will be summarized with subject counts and percentages/rates, and where applicable, with exact 95% Clopper-Pearson² confidence intervals. The p-values will be based on either Pearson's Chi-square test or Fisher's exact test by checking the expected frequency for each cell in the maximum contingency table against Cochran's rule³ (i.e. if the expected frequencies for all cells are ≥ 5 , then Pearson's Chi-square test will be used, otherwise Fisher's exact test will be used).

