2.11 Multiplicity Issues

To control for type I error inflation, the test of secondary endpoints will be performed in a hierarchical order at two-sided 5% significance level:

1. Secondary endpoint #1
2. Secondary endpoint #2
3. Secondary endpoint #3
4. Secondary endpoint #4
5. Secondary endpoint #5
6. Secondary endpoint #6
7. Secondary endpoint #7

The secondary endpoints will be tested only if the superiority in the SCS group is demonstrated in the primary endpoint. If hypothesis testing for superiority of secondary endpoint #1 fails, no hypothesis testing for the rest of secondary endpoints, etc.

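### If the unblinded interim raises the sample size, the SAP names the weighted CHW statistic for the primary and secondaries #1 to #3 only, so the 5% level of #4 to #7 is not guaranteed

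*SAP*

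**What the plan says.** SAP 2.5 plans one interim analysis, when 70% of the Phase I randomized subjects reach 6 months. SAP 2.4 describes the task: "The unblinded independent statistician will perform the sample size re-estimation for 4 endpoints (1 primary and secondary endpoints #1, #2, and #3"). If the sample size is increased, SAP 2.5 says the CHW weighted statistic "will be used in the final analysis of the primary and secondary endpoints 1, 2, and 3". Details are deferred to Adaptive Design Plan CL1014964.

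SAP 2.11 lists all seven secondaries in one fixed sequence that starts only after the primary succeeds: "To control for type I error inflation, the test of secondary endpoints will be performed in a hierarchical order at two-sided 5% significance level".

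No adaptive method is given for #4 to #7. What remains for them is the general text. For continuous variables (#6, #7), SAP 2.2.1 says: "The p-values will be calculated based on either two-sample t-test or Wilcoxon rank sum test as appropriate". For categorical variables (#4, #5), SAP 2.2.2 says: "The p-values will be based on either Pearson's Chi-square test or Fisher's exact test".

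On the extra subjects, SAP 1.3 says: "Phase II is the continued access phase and will include up to 70 randomized subjects". The SAP does not state that 270 is the cap for re-estimation. Protocol 8.6 leaves multiplicity to the SAP, and Protocol 8.8 leaves the interim analysis to the Adaptive Design Plan.

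**The concern.** A fixed sequence controls the familywise error only if each test in it holds its own level. An ordinary final test holds its level when the sample size is fixed, or is changed for reasons independent of that endpoint's interim result. Here the final sample size may depend on unblinded NRS and ODI results by arm. Secondaries #4 to #7 are 6-month patient-reported outcomes in the same subjects, so their interim results are probably correlated with those that decide the increase. Adding subjects when the drivers look weak then tends to add them when #4 to #7 also look weak. The pooled test gives the new data more weight than planned, and this can change its error rate.

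The CHW statistic avoids this by fixing the stage weights in advance. The sponsor already uses it beyond the primary, for #1 to #3, and the documents give no reason to stop there within a single hierarchy. At stake is whether a positive result on #4 to #7 after an increase can be presented as controlled at 5%, as SAP 2.11 implies.

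**Working it through.** **Inputs from the SAP.** Response rates 45% and 20%, ratio 3:2, 25% attrition, "Two-sided alpha of 0.05", unpooled Z-test, 200 subjects in Phase I and up to 70 in Phase II (2.4); interim at 70% (2.5); sequence at two-sided 5% (2.11).

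**Assumptions of this review.** The maximum after re-estimation is 270 (235 as a variant). The correlation r between the driving endpoint and a null endpoint among #4 to #7 is 0.5 to 0.7. The re-estimation rule is not in the documents, so the check uses the worst case over all rules and then six example rules.

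**1. The plan's own power.** 200 × 0.75 = 150 evaluable, that is 90 SCS and 60 CMM.
- SE = √(0.45×0.55/90 + 0.20×0.80/60) = 0.0736
- 0.25/0.0736 = 3.397; power = Φ(3.397 − 1.960) = 92.5%

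The stated figure of at least 90% reproduces.

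**2. How an increase can raise the error.** Take the limiting case r = 1. With interim statistic z1 on 140 subjects and final size N, the one-sided conditional error of the ordinary test is 1 − Φ((1.96√N − z1√140)/√(N − 140)). At z1 = 1:
- N = 200: (27.72 − 11.83)/7.746 = 2.051, error 0.0201
- N = 270: (32.21 − 11.83)/11.40 = 1.787, error 0.0370

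An increase to 270 raises the conditional error whenever z1 is below about 1.54.

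**3. Worst case over every rule, ignoring the hierarchy.** Given the driver's z1 under its null, the null endpoint's final Z has mean √(n1/N)·r·z1 and variance (n1(1 − r²) + n2)/N, with n1 = 140 and n2 from 60 to 130. Choosing n2 to maximise the two-sided rejection probability at each z1, and integrating over z1, gives:

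| r | cap 270 | cap 235 |
|---|---|---|
| 0 | 5.00% | 5.00% |
| 0.5 | 5.24% | 5.14% |
| 0.6 | 5.33% | – |
| 0.7 | 5.44% | 5.25% |
| 1.0 (theoretical bound) | 5.87% | – |

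**4. With the hierarchy in place.** A false claim needs the driver to succeed first (CHW above 1.96) and then the null endpoint's ordinary Z to exceed 1.96. One driver; increase to 270 when conditional power under the interim trend is below 0.8, below 0.9, or within 0.1–0.8, 0.3–0.8, 0.5–0.8 or 0.3–0.9; r from 0.5 to 0.7; 2,000,000 draws per case (simulation SE 0.0001). The target is 0.0250 one-sided.

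| Driver power at 200 | False-claim rate, ordinary test on the null endpoint |
|---|---|
| 92.5% (planned effect) | 0.0251–0.0254 |
| 80% | 0.0251–0.0258 |
| 50% | 0.0233–0.0268 |
| no driver effect | 0.0046–0.0087 |

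Numerical integration of the same quantities agrees to within 0.0001. With CHW (weights √0.7 and √0.3) on the null endpoint as well, the simulated rate never exceeds 0.0251.

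**5. Cost of CHW at 270.** Planned second stage 60, actual 130. Drift relative to the pooled test = (0.70 + √(0.30×0.65))/√1.35 = 0.9825. Squared, this is 0.9654, a loss of about 3.5% of information, or 0.035 × 270 ≈ 9 subjects. An endpoint with 80% power at 200 has 90.2% at 270 with the ordinary test and 89.2% with CHW. At 235 the information loss is about 1.2%.

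**The case against.** The strongest reply is that the SAP never says in words that #4 to #7 stay on ordinary tests. It defers details to the Adaptive Design Plan, which may cover these endpoints or restrict the rule so that little or no inflation arises. That stands as a limit. It does not remove the gap in the SAP, which names the CHW endpoints explicitly and leaves four members of the same hierarchy out.

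The second reply is that the effect is negligible, and on size this is largely right. The excess of about 0.2 percentage points needs 50% driver power, correlation near 0.7 and a rule with no lower limit on conditional power, all together. Limiting increases to conditional power of 0.5 to 0.8 gave at most 0.0255. At the planned effect, the two-sided level of the ordinary test without the hierarchy was 0.0480 to 0.0502, so there is essentially no inflation on that scale. The worst-case figures in step 3 ignore the hierarchy, count rejections in either direction and assume a cap that the SAP does not state. They are bounds, not expectations.

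Third, the consequence is limited. Study success rests on the primary alone (SAP 2.7), #4 to #7 come last in the sequence, and Protocol 4.3 lists PCS, PGIC and PROMIS-29 among descriptive endpoints. This supports a minor rating. It does not make the control described in SAP 2.11 complete.

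**Conclusion.** The point holds and is minor. After an unblinded increase, the SAP's stated tests do not guarantee 5% for secondaries #4 to #7, although SAP 2.11 offers the hierarchy as type I error control. Under the assumptions above, the excess over 0.0250 one-sided is near zero at the planned effect and at most about 0.2 percentage points in the scenarios tried. It can also be negative, and at zero correlation the ordinary test keeps its level. The actual size depends on the re-estimation rule and cap in the Adaptive Design Plan and on correlations the documents do not give. The issue arises only if the sample size is increased and the primary and #1 to #3 have all succeeded. The primary endpoint, #1 to #3 and the success criterion are untouched. This is a gap in guaranteed control, not a demonstrated large error.

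**What to change.** State in SAP 2.5, and align Adaptive Design Plan CL1014964, that if the sample size is increased, the CHW statistic with the prespecified stage weights is used for the primary and all secondary endpoints #1 to #7. Do this before the unblinded interim, because a method chosen afterwards is open to challenge.

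The cost is one sentence, the alignment of the second document, and stage-wise statistics for #4 to #7 from data already collected, plus the small efficiency loss in step 5 if an increase occurs. Without an increase nothing changes.

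If the sponsor prefers to keep ordinary tests, an acceptable alternative is to state that #4 to #7 fall outside confirmatory control after an increase. If the Adaptive Design Plan already covers them, the SAP should say so.
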